9.2 Sensitivity Analyses

9.2.1 Analysis for TOTPAR in Presence of Missing Data

For the TOTPAR analysis, missing pain relief assessments after first dose as well as pain relief assessments after start of intake of rescue medication, will be imputed by LOCF for intermittent missing data, and substitution by δ for missing data after premature discontinuation from the trial or disregarded pain relief assessments after start of rescue medication intake (Section 8.3 in SAP). Furthermore, to investigate whether results of the trial are sufficiently similar to results of past historical trials with respect to all design features that can influence the estimation of treatment effect (constancy assumption), single imputation methods used in historical trials of the active comparators diclofenac and tramadol will be applied as well, namely LOCF only, and LOCF for intermittent missing data and substitution by zero (no relief from baseline pain) for missing data after premature discontinuation from the trial or disregarded pain relief assessments after start of rescue medication intake (Section 8.3 in SAP). Finally additional WOCF+LOCF and WOCF only sensitivity analyses (Section 8.3 in SAP), are added to address the specific concern when rescue medication is given prior to the scheduled assessment time. Clearly, once rescue medication is given the pain levels will drop significantly and measurements post rescue medication are excluded from the analyses as well. These sensitivity analyses will enable the use of time points for subjects after their use of rescue medication by using their imputed values.

At the conclusion of imputation of the missing data based on each of the imputation methods, the same identical analysis as described for the primary endpoint (Section 9.1) will be once again conducted to examine the robustness of the outcome. This analysis will be conducted in the FAS population.

9.2.2 Alternate Analysis Population

The primary efficacy analysis will be repeated for the TOTPARs as a sensitivity analysis on the PPS. Additional sensitivity analyses and the analysis of additional efficacy parameters will be performed on the FAS only, unless otherwise specified.

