18.2 Justification of non-inferiority margin

On 30 Mar 2016, an updated literature search in PubMed yielded 7 publications, none of which provided elements that could serve to identify a rationale for a non-inferiority margin.

The search string used was (((third molar removal) OR third molar extraction) OR third molar surgery)) AND ((non-inferiority) OR clinically relevant difference).

Farrar (2000) has pointed out that the absence of taking a next dose or a dose of rescue medication, under the assumption that these can be taken freely, can be seen as the patient's most unambiguous way to express that his/her perceived pain relief is evaluated by him/her as sufficient. In a series of repeated experiments mainly in cancer breakthrough pain, Farrar has concluded that a mean TOTPAR equal to 33% of the maximum possible TOTPAR has the optimal combination of sensitivity and specificity to predict that a patient does not feel the need to take another dose of analgesic (Farrar et al. 2010). Because the maximum value for TOTPAR₄ = 16 and following Farrar's approach, a TOTPAR₄ = 5.33 would be a clinically relevant effect, though not necessarily a minimum clinically relevant effect.

Clinical trials in pain are known for their relevant placebo effect which has to be taken into account when proposing a clinically relevant difference to placebo. A mean TOTPAR₄ value of 2.37 was found for placebo by pooling across all trials in pain after third molar removal with diclofenac 50 mg, as available in the public domain (Bakshi et al. 1994), or with any dose of tramadol available at Grünenthal in-house (Reports ICSR031-00, ICSR033-00, TRAMAP-ANAG-02, TRAMAP-ANAG-07, TRAMAP-ANAG-10, TRAMAP-ANAG-12, TRAMAP-ANAG-13, CAPSS-128). Thus, a difference to placebo in TOTPAR₄ value by 5.33-2.37 = 2.96 ≈ 3 can be assumed to represent a clinically relevant difference, although not necessarily a minimum clinically relevant difference.

We believe that a choice of a non-inferiority margin $\Delta = 0.5 * 3 = 1.5$ (½ of the clinically meaningful effect of 3 points TOTPAR₄) reflects the largest loss of effect that would still be clinically acceptable.

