4. DETERMINATION OF SAMPLE SIZE

A total number of 720 subjects or 180 subjects per treatment group are required to achieve an overall power of at least 85% to reject the null hypothesis of at least 1 of the 4 formal statistical tests in the primary analysis of the trial (1-sided t-test, type I error of $\alpha/4$ with $\alpha = 2.5\%$) assuming a common standard deviation of change from baseline values of 4 points (TOTPAR4) and an expected treatment difference of at least 2 points (TOTPAR4) on the primary efficacy endpoint in the comparisons between tramadol HCl/diclofenac sodium 50 mg/50 mg and the monotherapies of diclofenac sodium 50 mg and tramadol HCl 50 mg, and using a non-inferiority margin of $\Delta = 1.5$ points (TOTPAR4) on the primary efficacy endpoint in the comparisons between tramadol HCl/diclofenac sodium 25 mg/25 mg and the monotherapies of diclofenac sodium 50 mg and tramadol HCl 50 mg. To achieve 180 evaluable subjects per arm and accounting that up to 10% of subjects will not be evaluable for the analysis set for the primary analysis, 200 subjects per arm or 800 subjects in total will be allocated to IMP.

Assuming an enrollment failure rate of about 25% which is usually observed in clinical trials in Mexico, about 1065 subjects are planned to be enrolled (i.e., sign the informed consent) in order to allocate 800 subjects to IMP, i.e., about 130 subjects per trial site in approximately 8 sites.

In summary, the study will be conducted at approximately 8 investigational sites in Mexico, and approximately 1065 patients will be enrolled.

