Appendix C: List of Tables, Figures, and Listings

List of Tables

Table Number	Table Description
14.1.1.1	Subject Disposition (All Subjects)
14.1.1.2	Subject Disposition by Site (All Subjects)
14.1.2.1	Early Discontinuation of Study Drug by Time Period (Safety Set)
14.1.2.2	Early Discontinuation of Study Drug by Time Period (FAS)
14.1.3	Protocol Deviations (FAS)
14.1.4.1	Demographic and Baseline Characteristics (Safety Set)
14.1.4.2	Demographic and Baseline Characteristics (FAS)
14.1.4.3	Demographic and Baseline Characteristics (PPS)
14.1.5.1	Medical History at Baseline (Safety)
14.1.5.2	Medical History at Baseline (FAS)
14.1.5.3	Medical History at Baseline (PPS)
14.1.6	Physical Examination at Baseline (Safety Set)
14.1.7.1	Prior Medications (Safety Set)
14.1.7.2	Prior Medications (FAS)
14.1.7.3	Prior Medications (PPS)
14.1.8.1	Concomitant Medications (Safety Set)
14.1.8.2	Concomitant Medications (FAS)
14.1.8.3	Concomitant Medications (PPS)
14.1.9.1	Study Drug Exposure (Safety Set)
14.2.1.1	Total Pain Relief through 4 Hours (TOTPAR4) (LOCF and Delta Substitution) (FAS)
14.2.1.2	Total Pain Relief through 4 Hours (TOTPAR4) (LOCF and Delta Substitution) (PPS)
14.2.1.3	Total Pain Relief through 4 Hours (TOTPAR4) (LOCF Only) (FAS)
14.2.1.4	Total Pain Relief through 4 Hours (TOTPAR4) (LOCF and Zero Substitution) (FAS)
14.2.1.5	Total Pain Relief through 4 Hours (TOTPAR4) (WOCF and LOCF) (FAS)
14.2.1.6	Total Pain Relief through 4 Hours (TOTPAR4) (WOCF Only) (FAS)
14.2.2.1	Total Pain Relief through 6 Hours (TOTPAR6) (LOCF and Delta Substitution) (FAS)
14.2.2.2	Total Pain Relief through 6 Hours (TOTPAR6) (LOCF and Delta Substitution) (PPS)
14.2.2.3	Total Pain Relief through 6 Hours (TOTPAR6) (LOCF Only) (FAS)
14.2.2.4	Total Pain Relief through 6 Hours (TOTPAR6) (LOCF and Zero Substitution) (FAS)
14.2.2.5	Total Pain Relief through 6 Hours (TOTPAR6) (WOCF and LOCF) (FAS)
14.2.2.6	Total Pain Relief through 6 Hours (TOTPAR6) (WOCF Only) (FAS)

Table Number	Table Description
14.2.3.1	Total Pain Relief through 8 Hours (TOTPAR8) (LOCF and Delta Substitution) (FAS)
14.2.3.2	Total Pain Relief through 8 Hours (TOTPAR8) (LOCF and Delta Substitution) (PPS)
14.2.3.3	Total Pain Relief through 8 Hours (TOTPAR8) (LOCF Only) (FAS)
14.2.3.4	Total Pain Relief through 8 Hours (TOTPAR8) (LOCF and Zero Substitution) (FAS)
14.2.3.5	Total Pain Relief through 8 Hours (TOTPAR8) (WOCF and LOCF) (FAS)
14.2.3.6	Total Pain Relief through 8 Hours (TOTPAR8) (WOCF Only) (FAS)

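### SAP 9.2.1 and 9.2.2, read literally, carry the non-inferiority tests with Δ = 1.5 to TOTPAR6 and TOTPAR8, for which no margin exists; SAP 9.3 carries over only the model

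*SAP*

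**What the plan says.** **The margin.** Protocol 18.2 takes one third of the TOTPAR4 maximum, subtracts a pooled placebo TOTPAR4 mean, and halves the result. It concludes that 1.5 "reflects the largest loss of effect that would still be clinically acceptable". Protocol 14.1.1 and SAP 4 label the 1.5 in TOTPAR4 points. The note under Table 1 in SAP 9.1 gives Δ = 1.5 with no hour or scale attached.

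**The primary analysis.** SAP 9.1 puts three things under the primary efficacy analysis: tests T1 to T4, the Bonferroni-Holm steps, and an ANCOVA with treatment, site and baseline pain. T3 and T4 are the non-inferiority tests of 25 mg/25 mg, and they are the only hypotheses written for that dose.

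**The repeats.** SAP 9.2.2 says: "The primary efficacy analysis will be repeated for the TOTPARs as a sensitivity analysis on the PPS". SAP 9.2.1 says that, after each imputation, "the same identical analysis as described for the primary endpoint (Section 9.1) will be once again conducted to examine the robustness of the outcome". It refers for the imputations to SAP 8.3, which names TOTPAR4, TOTPAR6 and TOTPAR8. Appendix C lists TOTPAR6 and TOTPAR8 tables for all five imputation methods on the FAS and one each on the PPS, for example "Total Pain Relief through 8 Hours (TOTPAR8) (LOCF and Delta Substitution) (PPS".

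**The narrower wording.** SAP 9.3 analyses the TOTPARs with the primary endpoint's ANCOVA model and leaves alpha unadjusted. Protocol 14.5.4 carries over the model and the missing-data handling to TOTPAR6 and TOTPAR8. Neither mentions T3, T4 or a margin.

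**The concern.** TOTPAR is a sum over time, so its points mean different things at 4, 6 and 8 hours. A fixed 1.5 points is a smaller loss of relief per hour the longer the window. If the Section 9.1 analysis is repeated unchanged, the 25 mg/25 mg arm faces a stricter test at 6 and 8 hours than at 4, and no one has justified that strictness.

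The practical stake is a misleading secondary result. With the same relief per hour in every arm, 25 mg/25 mg could meet the margin at 4 hours and miss it at 8 because of the units. Since the second dose is due at 8 hours, a reader could take the miss as effect wearing off before that dose. A programmer working from the SAP must either use 1.5 or invent a rule after the fact.

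**Working it through.** **1. Reproduce the plan's own figure.** SAP 4 states that "720 subjects or 180 subjects per treatment group are required", for an "overall power of at least 85% to reject the null hypothesis of at least 1 of the 4 formal statistical tests", "assuming a common standard deviation of change from baseline values of 4 points (TOTPAR4". Inputs: one-sided α/4 = 0.625%, SD 4, margin 1.5. The true difference for the non-inferiority tests is not stated; I assume 0.

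Power of one non-inferiority test = Φ(Δ / (SD × √(2/n)) − z₁₋α).

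With n = 180: SE = 4 × √(2/180) = 0.4216; 1.5 / 0.4216 = 3.558; minus 2.498; power 85.5%. The noncentral t calculation gives 85.2%, and 180 is the smallest n that reaches 85%. The stated 180 is reproduced. It rests on a single TOTPAR4 non-inferiority test; the chance of rejecting at least one of the four is higher, so the plan's claim of at least 85% holds.

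**2. The margin as a share of the range.** Relief scores run from 0 to 4, so the maximum is 4 × hours: 16 (stated in SAP 8.1.1), 24 and 32.

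- TOTPAR4: 1.5/16 = 9.4%
- TOTPAR6: 1.5/24 = 6.25%
- TOTPAR8: 1.5/32 = 4.7%

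As average relief over the window this is 1.5/4 = 0.375, 1.5/6 = 0.25 and 1.5/8 = 0.19 points on the 0–4 scale.

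**3. Power if 1.5 is used unscaled.** The level is one-sided 2.5% (z = 1.960), because SAP 9.3 leaves secondary alpha unadjusted; n = 180 per arm, analysed difference 0. The documents give an SD only for TOTPAR4, so those at 6 and 8 hours are assumptions. The larger value grows in proportion to time, and the smaller is a milder case.

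| Endpoint | SD | SE | 1.5/SE | Power |
|---|---|---|---|---|
| TOTPAR4 | 4 (stated) | 0.422 | 3.558 | 94.5% |
| TOTPAR6 | 5.5 | 0.580 | 2.587 | 73.5% |
| TOTPAR6 | 6 | 0.632 | 2.372 | 66.0% |
| TOTPAR8 | 7 | 0.738 | 2.033 | 52.9% |
| TOTPAR8 | 8 | 0.843 | 1.779 | 42.8% |

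If the SD stayed at 4 at 6 and 8 hours, power would remain 94.5%.

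**4. Can a margin be derived at 6 and 8 hours?** The 18.2 rule is ½ × (maximum/3 − placebo mean). At 4 hours: ½ × (5.33 − 2.37) = 1.48, which the protocol rounds to 1.5. No placebo mean is given at 6 or 8 hours, so two assumptions bracket the answer:

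- 6 hours: ½ × (8 − 3.56) = 2.22 if placebo relief accrues in proportion to time; ½ × (8 − 2.37) = 2.82 if it stays at 2.37.
- 8 hours: ½ × (10.67 − 4.74) = 2.96; or ½ × (10.67 − 2.37) = 4.15.

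The ranges are too wide to fix a margin from the documents.

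**5. The imputation works in the same direction.** After rescue, SAP 8.3.1 gives the monotherapy arms 0.375 and the combination arms 0. Protocol 14.5.5 sized the 0.375 so that rescue at 2 hours costs Δ/2 on TOTPAR4. For a monotherapy subject rescued at 2 hours, the gain is 0.375 × (hours − 2): 0.75 at 4 hours, 1.5 at 6 and 2.25 at 8. That is 50%, 100% and 150% of 1.5. In the delta-substitution tables, equal relief and equal rescue would therefore not give a difference of 0, and the powers in step 3 are optimistic there.

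**The case against.** The strongest reply is that nothing in either document says outright that T3, T4 or the value 1.5 is used at 6 or 8 hours. Table 1 lists the tests of the primary objective, whose endpoint is TOTPAR4. SAP 9.1 also says that the primary analysis uses an ANCOVA model, so repeating it could mean repeating the model alone, as SAP 9.3 and protocol 14.5.4 have it. The Appendix C titles mention no margin or hypothesis. This stands. A reader might infer that the SAP definitely judges non-inferiority at 6 and 8 hours against 1.5, and the text does not support that.

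It does not remove the point. Where the SAP means the model only, in 9.2.3, 9.3 and 9.4, it says so; 9.2.1 and 9.2.2 are broader. Step 4 of the Holm procedure also moves on to formal tests of secondary null hypotheses, and none is written out.

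Three further inferences should be resisted:

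- **Power figures at α/4.** On the same SDs these would be about 45–54% at 6 hours and 24–32% at 8. SAP 9.3 leaves secondary alpha unadjusted, so the 2.5% figures are the fairer ones.
- **An easier claim of non-inferiority.** A margin of 1.5 on a wider scale is stricter, so it cannot make a false claim easier.
- **Margins of 2.25 and 3.0 as a cure.** Holding the share of the range at 9.4% is not the 18.2 rule, and the delta imputation shifts the contrast against the combination. These margins would not reliably restore the power seen at 4 hours.

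**Conclusion.** The passages do not agree. Taken literally, SAP 9.2.1 and 9.2.2 apply a TOTPAR4 margin to TOTPAR6 and TOTPAR8; SAP 9.3 and protocol 14.5.4 do not. If 1.5 is used unscaled, a single non-inferiority test of 25 mg/25 mg loses roughly 21 to 28 percentage points of power at 6 hours and 42 to 52 at 8. This assumes SDs of 5.5–6 and 7–8, an analysed difference of 0, 180 per arm and one-sided 2.5%. The loss is nil if the SD stays at 4.

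The consequence is a false failure in secondary and sensitivity tables. A reader might infer a threat to the trial's main conclusion, but the TOTPAR4 tests, their Holm control, the sample size and the rule for a positive trial are untouched. It should be corrected before unblinding, but it does not undermine the design.

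**What to change.** State in SAP 9.2.1, 9.2.2 and 9.3 that T3, T4 and Δ = 1.5 apply to TOTPAR4 only. In every TOTPAR6 and TOTPAR8 table, on the FAS and the PPS, report the 25 mg/25 mg contrasts as LS mean differences with 95% CIs from the same ANCOVA, with no non-inferiority verdict. Set no margin at 6 or 8 hours, because the documents give no placebo mean there from which to derive one.

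The cost is a few sentences in the SAP and fewer p-values in those tables. Data, design and sample size do not change. The downside is that the trial will make no formal non-inferiority statement at 6 and 8 hours.

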9.2.3 Subgroup Analyses

Pain intensity will be evaluated based on the following scale: None (score = 0), Mild ($1 < \text{score} < 5$), Moderate ($5 < \text{score} < 6$), and Severe ($\text{score} > 7$). However subject inclusion criteria at baseline require pain intensity level of Moderate or Severe after the surgical procedure. Subgroup analyses will be performed on TOTPAR4 for subjects with a moderate pain intensity (score = 5 or 6) at baseline and for subjects with a severe pain intensity (score = 7, 8, 9, 10) at baseline. Furthermore, subgroup analyses will be performed per site for TOTPAR4, TOTPAR6, and TOTPAR8. These analyses will follow the same ANCOVA model as stated before. The by-site analyses will additionally include a site-by-treatment interaction factor in the model, and besides the FAS, will also be performed on the PPS. In all of these cases, the TOTPARs used will be those based upon imputations using the LOCF and delta substitution method.

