14.5.6 Subgroup analyses

Subgroup analyses will be performed for subjects with a moderate pain intensity at baseline (with scores of 5 or 6 on the 11-point NRS) and for subjects with a severe pain intensity at baseline (with scores of 7 to 10 on the 11-point NRS). Furthermore, subgroup analyses will be performed per site.

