ADL Adorlan (tramadol HCl/diclofenac sodium); D diclofenac sodium; T tramadol hydrochloride; HCl hydrochloride. $\Delta = 1.5$ is the non inferiority margin.

The trial will be positive if at least 1 of the according 4 statistical tests rejects the according null hypothesis.

According to the Bonferroni-Holm procedure, the p-values of the 4 tests T_1 , T_2 , T_3 , and T_4 will be sorted in ascending order $p_{(1)} < p_{(2)} < p_{(3)} < p_{(4)}$ and the following algorithm will be applied to the corresponding null hypotheses $H_{(01)}$, $H_{(02)}$, $H_{(03)}$, $H_{(04)}$:

- Step 1. If $p_{(1)} < \alpha/4$ (0.625%), reject $H_{(01)}$ and move to the next step. Otherwise retain all null hypotheses and stop.
- Step 2. If $p_{(2)} < \alpha/3$ (0.833%), reject $H_{(02)}$ and move to the next step. Otherwise retain $H_{(02)}$, $H_{(03)}$ and $H_{(04)}$ and stop.
- Step 3. If $p_{(3)} < \alpha/2$ (1.25%), reject $H_{(03)}$ and move to the next step. Otherwise retain $H_{(03)}$ and $H_{(04)}$ and stop.
- Step 4. If $p_{(4)} < \alpha$ (2.5%), reject $H_{(04)}$ and move to formally testing null hypotheses related to secondary endpoints. Otherwise retain $H_{(04)}$.

The primary analysis will use an ANCOVA model with treatment, site, and baseline pain (measured on an 11-point NRS) as covariates. The pain intensity score assessed before IMP intake will be considered the baseline pain intensity and site will be used as a covariate.

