14.2.4.1	Total Pain Relief through 4 Hours (TOTPAR4) (LOCF and Delta Substitution) (FAS in Subjects with Moderate Pain Intensity)
14.2.4.2	Total Pain Relief through 4 Hours (TOTPAR4) (LOCF and Delta Substitution) (FAS in Subjects with Severe Pain Intensity)
14.2.5.1	Total Pain Relief through 4 hours (TOTPAR4) by Site (LOCF and Delta Substitution) (FAS)
14.2.5.2	Total Pain Relief through 4 hours (TOTPAR4) by Site (LOCF and Delta Substitution) (PPS)
14.2.5.3	Total Pain Relief through 6 hours (TOTPAR6) by Site (LOCF and Delta Substitution) (FAS)
14.2.5.4	Total Pain Relief through 6 hours (TOTPAR6) by Site (LOCF and Delta Substitution) (PPS)
14.2.5.5	Total Pain Relief through 8 hours (TOTPAR8) by Site (LOCF and Delta Substitution) (FAS)
14.2.5.6	Total Pain Relief through 8 hours (TOTPAR8) by Site (LOCF and Delta Substitution) (PPS)
14.2.6.1	Pain Relief Score after First Dose over Time (FAS)
14.2.6.2	Pain Intensity Score after First Dose over Time (FAS)
14.2.6.3	Pain Intensity Difference (PID) after First Dose over Time (FAS)
14.2.6.4	Summed Pain Intensity Difference (SPID) after First Dose over Time (FAS)
14.2.7.1	Peak Pain Relief Score (FAS)
14.2.7.2	Peak Pain Intensity Difference (FAS)
14.2.8.1	Time to Achieve a 50% Reduction of Baseline Pain (FAS)
14.2.8.2	Time to Onset of First Perceptible Pain Relief (FAS)
14.2.8.3	Time to Onset of Meaningful Pain Relief (FAS)
14.2.8.4	Time to Request of First Rescue Medication (FAS)
14.2.8.5	Time to Intake of First Rescue Medication (FAS)
14.2.8.6	Time to Peak Pain Relief Score (FAS)
14.2.8.7	Time to Peak Pain Intensity Difference Score (FAS)
14.2.9.1	Subject's Global Evaluation of the Treatment (FAS)
14.3.1.1	Overall Summary of All Adverse Events (Safety Set)
14.3.1.2	Treatment-Emergent Adverse Events by System Organ Class and Preferred Term (Safety Set)

Table Number	Table Description
14.3.1.3	Non Treatment-Emergent Adverse Events by System Organ Class and Preferred Term (Safety Set)
14.3.1.4	Treatment-Emergent Adverse Events by System Organ Class, Preferred Term and Severity (Safety Set)
14.3.1.5	Treatment-Emergent Adverse Events by System Organ Class, Preferred Term and Relationship to IMP or Rescue Medication (Safety Set)
14.3.1.6	Treatment-Emergent Severe Adverse Events by System Organ Class and Preferred Term (Safety Set)
14.3.1.7	Treatment-Emergent Adverse Events Leading to Dose Reduction by System Organ Class and Preferred Term (Safety Set)

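### The plan analyses moderate and severe baseline pain in separate models and never estimates whether the treatment effect differs between them

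*SAP*

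**What the plan says.** Protocol 10.3 stratifies randomisation by site and by baseline pain category (moderate or severe). Protocol 14.5.6 then plans that "Subgroup analyses will be performed for subjects with a moderate pain intensity at baseline", with the same for severe pain and for each site, and gives no model.

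SAP 9.2.3 is more specific: "Subgroup analyses will be performed on TOTPAR4 for subjects with a moderate pain intensity (score = 5 or 6) at baseline", and likewise for scores 7 to 10. On the model it says: "These analyses will follow the same ANCOVA model as stated before". The model meant is that of SAP 9.1: "The primary analysis will use an ANCOVA model with treatment, site, and baseline pain (measured on an 11-point NRS) as covariates". It contains no interaction.

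The next sentence of SAP 9.2.3 does add one, but for site: "The by-site analyses will additionally include a site-by-treatment interaction factor in the model". Nothing equivalent is given for severity in SAP 8.5, SAP 9.2.3 or the list of changes in SAP 11. The table list in SAP Appendix C agrees with this reading. Table 14.2.4.1 is labelled "FAS in Subjects with Moderate Pain Intensity", Table 14.2.4.2 is its counterpart for severe pain, and no table compares the two.

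Neither document gives an alpha, a decision rule, an expected moderate-to-severe split, or a rule for judging consistency between the strata.

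**The concern.** Two separate fits each estimate the treatment effect within one stratum. Neither estimates the difference between the two effects, which is what a subgroup analysis by severity is meant to inform. Baseline NRS as a main effect adjusts the outcome for starting pain, but does not let the treatment effect vary with it.

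The question is foreseeable. The trial enrols moderate to severe pain, supports registration (Protocol 6.3), and uses severity as a stratum. With two stand-alone tables, the natural way to answer it is to see whether each stratum meets the non-inferiority margin or reaches superiority. Each stratum has only part of the sample, so the two verdicts can disagree by chance when the true effects are the same. The result could then be described as an effect in one severity group but not the other, with no estimate of that contrast behind it.

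**Working it through.** **Inputs from the documents (SAP 4, SAP 9.1).** SD 4 points; 180 evaluable per arm (200 allocated); non-inferiority margin 1.5; superiority difference 2; one-sided family alpha 2.5%, with alpha/4 = 0.625% in the sample-size calculation and at the first Holm step.

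**Assumptions, not in the documents.** The moderate-to-severe split (50:50, with 40:60 and 30:70 as a range); the alpha a reader would apply within a stratum (2.5% and 0.625% both shown); the same true effect in both strata. The true non-inferiority difference of 0 is not written, but the first step below shows that it reproduces the planned sample size.

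**Step 1: the plan's own figure.** SAP 4 states: "A total number of 720 subjects or 180 subjects per treatment group are required to achieve an overall power of at least 85" per cent. For one non-inferiority test at a true difference of 0 and one-sided 0.625%, the normal approximation gives 178 per arm. The noncentral t gives 180 per arm, with power 85.2% (179 gives just under 85%). The stated figure therefore reproduces as the power of a single non-inferiority comparison.

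**Step 2: power within a stratum.** Power = Φ(d / (4·√(2/n)) − z), where n is the number per arm in the stratum, d is the distance from the null, and z is 1.960 or 2.498. With n = 90, 4·√(2/90) = 0.596.
- Non-inferiority, d = 1.5: 1.5/0.596 = 2.516. Power is Φ(0.556) = 71.1% at 2.5% and Φ(0.018) = 50.7% at 0.625%.
- Superiority, d = 2: 2/0.596 = 3.354. Power is 91.8% and 80.4%.

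**Step 3: chance that one stratum passes and the other does not.** The strata are independent, so this is p1(1 − p2) + p2(1 − p1), or 2p(1 − p) for equal strata. For example, 2 × 0.711 × 0.289 = 41.1%.

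| Scenario, same true effect in both strata | Power per stratum, 2.5% | Discordant, 2.5% | Power per stratum, 0.625% | Discordant, 0.625% |
|---|---|---|---|---|
| Non-inferiority, difference 0, 180 per arm, 50:50 | 71.1% / 71.1% | 41.1% | 50.7% / 50.7% | 50.0% |
| As above, 40:60 | 61.4% / 78.7% | 43.5% | 40.2% / 60.2% | 52.0% |
| As above, 30:70 | 49.5% / 84.5% | 50.3% | 29.1% / 68.4% | 57.7% |
| As first row, 200 per arm | 75.5% / 75.5% | 37.0% | 56.1% / 56.1% | 49.3% |
| As first row, FDC 25/25 truly 0.5 better | 91.8% / 91.8% | 15.0% | 80.4% / 80.4% | 31.5% |
| As first row, FDC 25/25 truly 0.25 worse | 55.4% / 55.4% | 49.4% | 34.4% / 34.4% | 45.1% |
| Superiority, difference 2, 180 per arm, 50:50 | 91.8% / 91.8% | 15.0% | 80.4% / 80.4% | 31.5% |

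**Step 4: what a direct comparison would deliver.** For one pairwise comparison, the SE of the between-stratum difference in effect is 4·√(2/n1 + 2/n2).
- 50:50 (90 and 90): SE 0.843; 95% half-width 1.96 × 0.843 = 1.65; detectable at 80% power, two-sided 5%: (1.960 + 0.842) × 0.843 = 2.36 points.
- 30:70 (54 and 126): SE 0.920; half-width 1.80; detectable 2.58 points.

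Such a test flags identical effects 5% of the time, by construction.

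**The case against.** The strongest reply is that the documents contain no verdict within a stratum. The four tests, the Holm steps and the rule for a positive trial belong to the primary FAS analysis. The severity analyses sit under Sensitivity Analyses in SAP 9.2, and the sentence on them names a model, not a test. This stands. A reader might infer that the plan will declare success or failure in each stratum; the documents do not say so. The discordance figures describe what happens if readers compare verdicts.

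A reader might also infer that discordance would occur about half the time as a general fact. That needs alpha/4, which the documents attach to the four primary hypotheses and not to subgroups, together with an assumed split and a true difference of 0. At one-sided 2.5% and an even split the figure is 37% to 41%, and it is lower if the low-dose combination is truly better. The protocol's own summary of an earlier bunionectomy trial (Table 2) reports greater total pain relief at 4 hours for both combination groups than for diclofenac, so a positive difference is plausible for that comparison.

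Nor is discordance the expected outcome because power is halved. An even split halves the sample. Power for one non-inferiority test falls from about 85% to 51% at alpha/4, and from about 94% to 71% at 2.5%. With equal strata, 2p(1 − p) cannot exceed 50%. The figures also concern crossing a threshold; they do not mean that the estimates themselves would differ markedly.

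Finally, an interaction test here is weak, and independent strata allow the difference to be worked out by hand if estimates and standard errors are printed. Both points are fair. They argue for keeping the separate fits, which allow stratum-specific site effects and variances, and for adding a planned estimate with its interval. They do not justify leaving the contrast out.

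**Conclusion.** The gap is real and small. The SAP plans separate severity models and a treatment interaction for site only, so it provides no direct assessment of effect modification by its one clinical efficacy subgroup.

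If verdicts are compared, identical true effects would often look discordant. For non-inferiority at a true difference of 0, this ranges from 37% to 50% at one-sided 2.5% and from 49% to 58% at alpha/4, over splits from 50:50 to 30:70 at 180 per arm and an even split at 200 per arm. It drops to 15% and 32% if FDC 25/25 is truly 0.5 points better, and is also 15% and 32% for superiority with a true difference of 2. All of these rest on SD 4 and on a split and a subgroup alpha that the documents do not give.

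A reader might take this as a flaw in the primary analysis. It is not: the subgroups lie outside the Holm procedure, and the primary conclusion is unaffected. This is an inexpensive improvement to a supportive analysis.

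**What to change.** In SAP 9.2.3:
1. Keep the moderate and severe estimates for the four comparisons, each with a 95% CI.
2. Add one FAS model: the primary ANCOVA plus severity stratum and treatment-by-severity, using the same LOCF-with-delta data. For each of the four comparisons report the between-stratum difference in effect with its 95% CI, together with the interaction test.
3. State that no superiority or non-inferiority decision is made within a stratum, and that consistency is not judged by comparing verdicts.
4. Add the corresponding table to Appendix C.

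The cost is SAP wording and one table; no new data are needed. The limitation to state alongside is modest precision: a 95% half-width of about 1.65 points at 180 per arm with an even split, 1.80 at 30:70, and about 2.4 points detectable at 80% power with an even split. The half-width exceeds the 1.5-point margin and the detectable difference exceeds the assumed 2-point effect. The estimate and interval should therefore lead, and a non-significant interaction should not be read as evidence of equal effects. The pooled model shares site and baseline-pain terms and the residual variance across strata, so its between-stratum difference may not exactly equal the difference of the two separate estimates; a footnote can say so.

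The change should be made before unblinding, because SAP 5 labels analyses performed after the blind is broken as post hoc.
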